2. SYNOPSIS

Name of Sponsor/Company:

Sage Therapeutics, Inc. (hereafter referred to as Sage Therapeutics, or Sage)

Name of Investigational Product:

SAGE-718 Oral Tablet

Name of Active Ingredient:

SAGE-718

Title of Study:

An Open-Label Evaluation of the Safety and Tolerability of SAGE-718 in Participants with Mild Cognitive Impairment or Mild Dementia Due to Alzheimer's Disease

Number of Sites and Study Location: Approximately 5 sites in the US

[figure not shown]
Phase of Development: 2

Planned Duration for each Study Participant: Each participant's involvement will be approximately 7 weeks, including a maximum 2-week Screening Period, a 1-week Baseline Period, a 2-week Treatment Period, and a 2-week Follow-up Period.

Objectives:

Primary Objective

• To evaluate the safety and tolerability of orally administered SAGE-718 in participants with mild cognitive impairment (MCI) or mild dementia due to Alzheimer's disease (AD)

Endpoints:

Primary Endpoint

• Incidence of treatment-emergent adverse events (TEAEs)

Secondary Endpoint

 Change from baseline in vital signs, clinical laboratory analytes, electrocardiograms (ECGs), and responses on the Columbia–Suicide Severity Rating Scale (C-SSRS)

Study Description:

This is an open-label study evaluating the safety and tolerability of SAGE-718 and its effects on in participants with MCI or mild dementia due to AD. Eligible participants will have a confirmed diagnosis of MCI or mild dementia due to AD, according to the National Institute on Aging-Alzheimer's Association 2011 diagnostic guidelines, which will be confirmed via the Clinical Dementia Rating Dementia Staging Instrument® (CDR). Participants will self-administer 3.0 mg of SAGE-718 once daily in the morning for 14 days within 1 hour after initiating a meal containing approximately 30 g of fat. Dosing and morning food intake will be tracked in a participant diary. Assessments will be performed as outlined in the Schedule of Assessments (Table 2)

In the setting of public health advisories due to COVID-19, assessments scheduled to be conducted at the study site may be performed via telephone/video if feasible. For assessments that cannot be conducted by phone or video, an in-home visit may be conducted.

Screening Period

The Screening Period will begin with the informed consent process for prospective participants, including study partners. Subsequent screening assessments will be performed between Day -21 and Day -8 to determine eligibility, including but not limited to: assessments of vital

signs, clinical laboratory tests, electrocardiogram (ECG), magnetic resonance imaging (MRI) of the brain, and C-SSRS. An electroencephalogram (EEG) will also be performed for all participants during Screening. **Baseline Period** The Baseline Period will occur from Day -7 through Day -1. During this period, each participant will receive dietary counseling to aid in choosing a morning meal containing approximately 30 g of fat to consume prior to dosing. On Day -7 (±1 day), participants will visit the clinic for confirmation of continued eligibility and collection of baseline safety data. Additionally, participants will be trained on the use of a mobile data capture device to perform and to document . Participants will continue to complete these assessments daily during the Baseline Period, using the mobile device remotely (at home), with the support of a study partner. On Day -1, participants will return to the study site for confirmation of continued eligibility and collection of further baseline safety data. Treatment Period Beginning on Day 1 and continuing through Day 14, participants will self-administer 3.0 mg of SAGE-718 (as six 0.5-mg oral tablets), once per day in the morning within 1 hour after initiating a meal containing approximately 30 g of fat, in accordance with the guidelines provided in a nutritional information brochure. During this period, participants will continue to complete daily assessments of via mobile device either remotely (at home) or in the clinic (at scheduled in-clinic visits) and will track investigational product (IP) dosing and predose food intake in a participant diary. On Day 1, Day 7 (±1 day), and Day 14, participants will arrive at the clinic in the morning prior to IP dosing and completion of daily mobile device tasks. Following predose procedures (ie, body weight, vital signs, ECG, followed by blood and urine collection for clinical laboratory analyses,), participants will eat a morning meal, then take the IP and complete the mobile device tasks under staff supervision. At scheduled clinic visits during the Treatment Period, study staff will dispense a sufficient amount of SAGE-718 for daily administration until the next scheduled study visit. In addition to the clinic visits, study staff will contact participants by telephone on Day 4 to document any TEAEs and/or changes in concomitant medications. Follow-up Period Study staff will contact participants by telephone on Day 21 (±1 day) to document any TEAEs and/or changes in concomitant medications. Participants will return to the clinic on Day 28 (± 2 days) for a follow-up visit. Dose Evaluation Committee At any time during the study, Sage may elect to form a Dose Evaluation Committee (DEC). If convened, this DEC will review the available data and provide recommendations for adjusting the

At any time during the study, Sage may elect to form a Dose Evaluation Committee (DEC). If convened, this DEC will review the available data and provide recommendations for adjusting the dose, administration schedule, and/or food intake and make adjustments for subsequent participants, if appropriate (see Section 7.4.2).

Number of Participants (planned): Up to 22 participants will be dosed to obtain up to 20 participants that complete 14 days of dosing in this study. Additional participants may be dosed if the early discontinuation rate is >10%.

Eligibility Criteria:

Inclusion criteria

Each eligible participant must:

1. Be capable of providing informed consent

- 2. Have signed an informed consent form prior to any study-specific procedures being performed
- 3. Be willing and, in the opinion of the investigator, able to comply with study procedures
- 4. Be between the ages of 50 and 80 years, inclusive, at Screening
- 5. Meet the following criteria for MCI or mild dementia due to AD at Screening:
 - a. A memory complaint reported by the participant or his/her study partner
 - b. A CDR score of 0.5 to 1.0 (inclusive) with a memory box score \ge 0.5
 - c. Essentially preserved activities of daily living, in the opinion of the investigator
 - d. Brain MRI report, obtained within the 2 years preceding the Baseline Period, that is consistent with the diagnosis of AD-MCI with no clinically significant findings of non-AD pathology that could account for the observed cognitive impairment
- 6. Have a score of 15 to 24 (inclusive) on the Montreal Cognitive Assessment at Screening
- 7. Have an estimated premorbid IQ ≥85 (as assessed by the Test of Premorbid Functioning, performed at Screening)
- 8. Have a study partner who is reliable, competent, at least 18 years of age, willing to be available to the study center by phone, support study-specific activities, and accompany the participant to study visits as needed
- 9. Be ambulatory (use of assistance devices such as a walker or cane is acceptable; individuals requiring a wheelchair are excluded), able to travel to the study center, and in the opinion of the investigator likely to be able to continue to travel to the study center to complete study visits for the duration of the study
- 10. Have stable concomitant medication usage per the following criteria:
 - a. For psychotropic medications, including acetylcholinesterase inhibitors and other medications that are likely to have an effect on cognitive performance, the dose and frequency must remain stable for at least 12 weeks prior to the first IP administration and be expected to remain stable for the duration of the study
 - b. For all other concomitant medications, the dose and frequency must remain stable for at least 4 weeks prior to the first IP administration and be expected to remain stable for the duration of the study
- 11. Agree, if female, to use an acceptable highly effective method of contraception (as defined in Section 9.2.4) during participation in the study and for 30 days following the last dose of IP, unless she is postmenopausal (defined as no menses for 12 months without an alternative medical cause and confirmed by follicle stimulating hormone >40 mIU/mL), surgically sterile (hysterectomy or bilateral oophorectomy or bilateral salpingectomy), or does not engage in sexual relations which carry a risk of pregnancy
- 12. Agree, if male, to use an acceptable method of highly effective contraception (as defined in Section 9.2.4) during the 14-day Treatment Period and for 2 weeks after receiving the last dose of IP, unless the participant does not engage in sexual relations that carry a risk of pregnancy
- 13. Agree, if male, to abstain from sperm donation during the 14-day Treatment Period and for 2 weeks after receiving the last dose of IP
- 14. Agree to refrain from drugs of abuse and alcohol for the duration of the study

Exclusion Criteria

Each eligible participant must not:

- 1. Have participated previously in a clinical study of SAGE-718, or have used any other investigational drug, biologic, or device or have participated in a clinical drug, biologic, or device study within 30 days or 5 half-lives (whichever is longer) prior to Screening
- 2. Have a condition that precludes undergoing an MRI, in accordance with standard operating procedures at the imaging facility (eg, ferromagnetic metal in the body, claustrophobia), in a participant requiring MRI during Screening
- 3. Have clinically significant comorbid medical conditions, a chronic condition that is unstable or requires more than 2 medications to be controlled, or be taking concomitant medications that, in the opinion of the investigator, may make the participant unsuitable for inclusion or have the potential to compromise safety and/or compliance with study requirements
- 4. Have any medical or neurological condition (other than AD) that might be contributing to the participant's cognitive impairment or history of cognitive decline
- 5. Have a history of brain surgery, deep brain stimulation, a significant head injury causing loss of consciousness greater than 30 minutes, or hospitalization due to a brain injury
- 6. Have a history, presence, and/or current evidence of a clinically significant intracranial abnormality (eg, stroke, hemorrhage, space-occupying lesion, or other non-AD pathology) that is likely to call into question a primary clinical diagnosis of Alzheimer's Disease.
- 7. Have a history of possible or probable cerebral amyloid angiopathy, according to the Boston Criteria (Greenberg 1995)
- 8. Have a history of treatment with an anti-amyloid therapy (including biologics) without subsequent MRI demonstrating the absence of amyloid-related imaging abnormalities
- 9. Be receiving any of the following prohibited medications:
 - a. Medications with potent effects at the N-methyl-D-aspartate (NMDA) receptor, including amantadine, ketamine, cycloserine, or related compounds
 - b. Memantine within the 4 weeks prior to IP administration
 - c. Medications that inhibit cholesterol absorption (eg, ezetimibe)
 - d. Bile acid sequestrants (eg, colesevelam, colestipol, cholestyramine)
 - e. Other medications given at doses or in combinations that are likely to have a deleterious effect on cognitive performance, as described in the 2019 American Geriatrics Society Updated Beers® Criteria for Potentially Inappropriate Medication Use in Older Adults (American Geriatrics Society 2019)
 - f. Prescribed cannabis or other THC-containing substances
- 10. Have an alcohol or drug use disorder within the past 12 months, as per DSM-5 criteria
- 11. Have a history of seizures or epilepsy, with the exception of a single episode of febrile seizures in childhood
- 12. Have current or recent suicidality, defined as follows:
 - a. Suicidal ideation within the past month, as evidenced by a score of 4 (active suicidal ideation with some intent to act, without specific plan) or 5 (active suicidal ideation with specific plan and intent) on the C-SSRS during Screening or Baseline

- b. Suicidal behavior within the past year, as evidenced by a "Yes" on any of the 5 C-SSRS Suicidal Behavior Items (actual attempt, interrupted attempt, aborted attempt, preparatory acts, or behavior) on the C-SSRS during Screening or Baseline
- c. Participant presents a serious risk of suicide in the opinion of the investigator
- 13. Have any of the following clinically significant medical conditions:
 - a. Any clinically significant finding on 12-lead ECG during Screening or Baseline
 - b. Supine vital signs outside of the following ranges during Screening or Baseline; vital sign measurements may be repeated once for initial values outside these ranges:
 - c. Heart rate <50 or >100 bpm
 - d. Systolic blood pressure <100 or >160 mmHg
 - e. Diastolic blood pressure <60 or >100 mmHg
- 14. Have a history, presence, and/or current evidence of serologic positive results for HIV-1 or HIV-2
- 15. Have a positive pregnancy test or be lactating at Screening or Day -1
- 16. Be investigative site personnel, sponsor personnel, or an immediate member of their family (spouse, parent, child, or sibling whether biological or legally adopted)

Investigational Product Dosage and Mode of Administration: SAGE-718 3.0 mg will be -self-administered as six 0.5-mg oral tablets, once daily in the morning within 1 hour after initiating a meal containing approximately 30 g of fat.

Duration of Treatment: 14 days

Statistical Methods:

A separate statistical analysis plan (SAP) will provide a detailed description of the analyses to be performed in the study. The SAP will be finalized and approved prior to database lock.

General Considerations

Unless otherwise specified, baseline is defined as the last measurement prior to the first dose of IP. Continuous endpoints will be summarized with n, mean, standard deviation, median, minimum and maximum, Q1, and Q3. In addition, change from baseline values will be calculated at each time point and will be summarized using the same summary statistics. Out of range safety endpoints may be categorized as low or high, where applicable. For all categorical endpoints, summaries will include counts and percentages.

Analysis Sets

Safety Set will include all participants who were administered IP and will be used to describe the safety data.

Safety Analysis

Adverse events (AEs) will be coded using Medical Dictionary for Regulatory Activities with the overall incidence of AEs displayed by System Organ Class and preferred term. Incidence of TEAEs will also be presented by maximum severity, and relationship to IP. Data from vital signs, clinical laboratory analytes, ECGs, and C-SSRS will be summarized using descriptive statistics.

Sample Size Calculation

No formal sample size calculation was made for this study. Up to 20 participants completing 14 days of dosing are considered sufficient to assess preliminary safety and tolerability and for signal-finding of after 14 days of repeated daily dosing with SAGE-718.

Assuming a 10% dropout rate, approximately 22 total participants will be required to obtain 20 completers. Additional participants may be dosed if the early discontinuation rate is >10%.

Table 2: Schedule of Assessments

| Study Period | Screening Baseline | | Treatment | | | | Follow Up | | |
|---|--------------------|----------------|-----------|-----|-------|---------------|-----------|---------------|---|
| Study Day | D -21 to D -8 | D -7 (±1 d) | D -1 | D 1 | D 4 a | D 7 (±1 d) | | D 21 a (±1 d) | |
| Informed consent b | X | | | | | | | | |
| Inclusion/exclusion criteria | X | X | X | | | | | | |
| Medical history and demographics ^c | X | | | | | | | | |
| Body weight | X | | | X | | X | X | | X |
| Body height | X | | | | | | | | |
| CDR | X | | | | | | | | |
| Test of Premorbid Functioning | X | | | | | | | | |
| Vital signs ^d | X | X | X | X | | X | X | | X |
| Physical examination ^e | X | X | X | | | | X | | |
| EEG ^f | X | | | | | | | | |
| 12-lead ECG ^g | X | | X | X | | X | X | | X |
| C-SSRS h | X | X | X | X | | X | X | | X |
| Clinical laboratory tests i | X | | X | | | X | X | | X |
| Alcohol test j | X | X | | | | | | | |
| Urine drug test | X | X | X | X | | X | X | | |
| FSH test k | X | | | | | | | | |
| Pregnancy test ¹ | X | | X | | | | X | | X |
| Serology test ^m | X | | | | | | | | |
| MRI ⁿ | X | | | | | | | | |
| | | | | | | | | | |
| Participant training ^{p, q} | | X | X | | | | | | |

| Study Period | Screening | ng Baseline Treatment | | Follow Up | | | | | |
|--------------------------------------|------------------|-----------------------|------|-----------|-------|---------------|---------------|------------------|--|
| Study Day | D -21 to D -8 | D -7 (±1 d) | D -1 | D 1 | D 4 a | D 7 (±1 d) | D 14 or ET | D 21 a (±1 d) | |
| | | | | | | | | | |
| Remote assessments v | | X | | | | | | | |
| IP self-administration w | | X (once daily) | | | | | | | |
| IP dispensation x | | | | X | | X | | | |
| IP accountability ^y | X | | | | | | | | |
| Safety telephone call | | | | | X | | | X | |
| TEAEs/SAEs | | X | | | | | | | |
| Concomitant medications ^z | | | X | | | | | | |

Abbreviations: CDR = Clinical Dementia Rating Dementia Staging Instrument®; C-SSRS = Columbia—Suicide Severity Rating Scale; d = days; ECG = electrocardiogram; EEG = electrocardiogram; ET = early termination; FSH = follicle stimulating hormone; HIV = human immunodeficiency virus; IP = investigational product;

MRI = magnetic resonance imaging; PET = positron emission tomography;

SAE = serious adverse event; TEAE = treatment-emergent adverse event

Notes: In the event of ET, efforts should be made to collect the Day 14 visit assessments.

When scheduled for the same time point, procedures should be performed in the following order: vital signs, ECG, blood draws, morning meal, IP dosing, then any scheduled postdose and/or

In the setting of public health advisories due to COVID-19, assessments scheduled to be conducted at the study site may be performed via telephone/video if feasible. For assessments that cannot be conducted by phone or video, an in-home visit may be conducted. Information about COVID-19 diagnosis, treatment, and quarantine status will be collected with medical history, AEs, and prior and concomitant medications.

- a Day 4 and Day 21 visits will occur via scheduled telephone calls.
- b Both study partners and participants are to be consented during the Screening Period.
- c In addition to full medical history, all nonpharmacological methods (
 treat or prevent of AD are to be recorded.
- d Vital signs to include temperature, respiratory rate, heart rate, and blood pressure. Heart rate and blood pressure to be collected in supine position and standing position at all scheduled time points (see Section 12.1.4).
- e Full physical examination to be conducted at Screening, abbreviated examinations thereafter (see Section 12.1.3).
- f EEG to be performed for all participants during Screening. If indicated, an unscheduled 1-hour EEG will be performed for that participant (see Section 12.1.6).
- g ECG will be measured after the participant has been in the supine position for at least 5 minutes.
- h "Baseline/Screening" C-SSRS form at Screening and "Since Last Visit" C-SSRS form thereafter.
- i Samples for clinical laboratory assessments, detailed in Table 4, to be collected ≤2 hours prior to dosing during the Treatment Period, and any time of day at other time points. Participants are to be in a fasted state for screening assessments only.
- j Alcohol testing will be performed in the clinic, either by urine dipstick or breathalyzer.
- k To confirm self-reported postmenopausal status in women only.
- 1 Serum pregnancy tests for all female participants at Screening; urine pregnancy tests will be conducted for all female participants who are not postmenopausal or surgically sterile at other scheduled time points.
- m To include testing for hepatitis B and C, HIV-1, and HIV-2
- n Only in participants without an MRI report obtained within the 2 years preceding the Baseline Period

- q Participants and study partners will be trained to use all study-related software and devices. Additional guidance will be provided on choosing a meal with approximately 30 g of fat.
- r Includes select tests of the tests are to be performed postdose during the Treatment Period and at approximately the same time of day (±2 hours) throughout the study.
- s Includes
- t Measures directed to study partners may be administered by telephone or in person.
- v Daily reminders will be sent to participants to complete assessments of within 1 hour following IP administration, either remotely (at home) or in the clinic during the Treatment Period (with observation by study staff during scheduled clinic visits).
- w On visit days during the Treatment Period, participants will self-administer IP in the clinic under the supervision of study staff after the predose assessments and consumption of a morning meal.
- x Study staff will dispense sufficient IP for daily dosing at home until the next scheduled visit (see Section 9.4).
- y On Days 7 and 14, participants will return used IP packaging and any unused IP for site staff to document.
- z At Screening, include all psychotropic medications used within 12 weeks of informed consent, any other medications and supplements taken within 60 days of informed consent, and all medication used to treat AD, regardless of timing. After Screening, all changes to any medication or supplements should be captured.

| 3. | TABLE OF CONTENTS, LIST OF TABLES, AND LIST OF FIGURES | |
|--------|--|----|
| 1. | TITLE PAGE | 1 |
| 2. | SYNOPSIS | 5 |
| 3. | TABLE OF CONTENTS, LIST OF TABLES, AND LIST OF FIGURES | 16 |
| 4. | LIST OF ABBREVIATIONS AND DEFINITIONS OF TERMS | 21 |
| 5. | INTRODUCTION | 22 |
| 6. | STUDY OBJECTIVES AND ENDPOINTS | 23 |
| 6.1. | Study Objectives | 23 |
| 6.1.1. | Primary Objective | 23 |
| | | |
| 6.2. | Endpoints | 23 |
| 6.2.1. | Primary Endpoint | 23 |
| 6.2.2. | Secondary Endpoint | 23 |
| | | |
| 7. | INVESTIGATIONAL PLAN | 24 |

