12.1.7. Laboratory Assessments

Blood and urine samples for clinical laboratory assessments will be collected. will be collected for hematology, biochemistry, coagulation, urinalysis, and serology at the time points detailed in Table 2 and Table 3.

During Screening only, samples for clinical laboratory assessments will be collected from participants when they are in a fasted state.

Analytes to be evaluated are summarized in Table 4.

Table 4: Summary of Clinical Laboratory Analytes

| Biochemistry | Renal Panel: glucose, calcium, phosphorus, blood urea nitrogen, creatinine, sodium, potassium, chloride, bicarbonate |
|--------------|---|
| | Hepatic Panel: albumin, ALT, AST, total bilirubin, direct bilirubin, indirect bilirubin, alkaline phosphatase, total protein, lactate dehydrogenase, gamma glutamyl transferase |
| | Other: triglycerides, cholesterol (LDL, HDL), creatine phosphokinase, thyroid stimulating hormone |

| Coagulation | activated partial thromboplastin time, prothrombin time, and international normalized ratio |
|------------------------------|---|
| Hematology | red blood cell count (RBC), hemoglobin, hematocrit, white blood cell count with differential, platelet count, and if RBC indices are abnormal, reflex RBC morphology is indicated |
| Urinalysis | protein, glucose, pH, blood, leukocytes, leukocyte esterase, urobilinogen, bilirubin, ketones, nitrite |
| Serology (screening only) | hepatitis B surface antigen, hepatitis C IgM antibody, HIV-1 antibody, HIV-2 antibody |

Follicle stimulating hormone testing will be conducted to confirm whether a participant with ≥12 months of spontaneous amenorrhea meets the protocol-defined criteria for being postmenopausal.

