### 16.2 Clinical Laboratory Evaluations

Laboratory assessments for biochemistry, coagulation, hematology, urinalysis, and serology, will be collected at screening, Day -1, Day 7, Day 14, and Day 28. The clinical laboratory tests to be performed for monitoring safety are listed in **Table 4**. Laboratory assessments will be summarized (n, mean, std,

median, Q1, Q3, minimum, and maximum) along with the change from baseline by each scheduled post-baseline visit. The International System of Unit (SI) will be used.

For the laboratory results that is "< or = x", where x is a number as collected in the data, the numeric part of the result will be used in the calculation in the summary tables. The same is true if the result is presented as below limit of quantification (BLQ) and a lower limit of quantification (LLOQ) value is provided – LLOQ value will be used for calculation in the summary tables. The actual results as collected will be displayed in the listings.

Summary tables on lab parameters will include descriptive statistics for the observed values and changes from baseline by scheduled assessment timepoint in hematology, serum chemistry, coagulation, and quantitative urinalysis test results.

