# 19.6 Appendix-F Tables, Figures, and Listings

Table Number Title Population

Table 14.1.1.1	Subject Analysis Sets	All Screened Subjects
Table 14.1.1.2	Subject Disposition	Safety Analysis Set
Table 14.1.1.3	Major Protocol Deviations	Full Analysis Set
Table 14.1.2.1	Demographic Characteristics	Safety Analysis Set
Table 14.1.3	Prior Medications by ATC Classification and WHO Drug Dictionary Preferred Term	Safety Analysis Set
Table 14.1.4	Concomitant Medications by ATC Classification and WHO Drug Dictionary Preferred Term	Safety Analysis Set
Table 14.1.5	Medical and Procedures by System Organ Class and Preferred Term	Safety Analysis Set
Table 14.1.6	Medical and Surgical History that are Ongoing at the time of Screening by WHO Drug Dictionary Preferred Term	Safety Analysis Set
Table 14.1.7	Alzheimer Disease History	Safety Analysis Set
Table 14.1.8	Summary of Exposure and Adherence	Safety Analysis Set

[figure not shown]

Table 14.3.1.1	Overall Summary of Treatment-Emergent Adverse Events	Safety Analysis Set
Table 14.3.1.2	Treatment-Emergent Adverse Events by System Organ Class and Preferred Term	Safety Analysis Set
Table 14.3.1.3	Treatment-Emergent Adverse Events Leading to Discontinuation of the Study by System Organ Class and Preferred Term	Safety Analysis Set
Table 14.3.1.4	Treatment-Emergent Adverse Events Leading to Interruption of Study treatment	Safety Analysis Set
Table 14.3.1.5	Treatment-Emergent Serious Adverse Events by System Organ Class and Preferred Term	Safety Analysis Set
Table 14.3.1.6	Treatment-Emergent Adverse Events with Outcome of Death by System Organ Class and Preferred Term	Safety Analysis Set
Table 14.3.1.7	Treatment-Emergent Adverse Events Leading to Discontinuation of Study Treatment by System Organ Class and Preferred Term	Safety Analysis Set
Table 14.3.1.8	Treatment-Emergent Adverse Events by System Organ Class, Preferred Term, and Relationship to IP	Safety Analysis Set
Table 14.3.1.9	Treatment-Emergent Adverse Events by System Organ Class, Preferred Term, and Maximum Severity	Safety Analysis Set

	1100	DC01110. 7 10-CNA-201
Table 14.3.3.1.1	Hematology and Coagulation Results by Time Point	Safety Analysis Set
Table 14.3.3.1.2	Potentially Clinically Important Postbaseline Hematology Results by Time Point	Safety Analysis Set
Table 14.3.3.2.1	Biochemistry Results by Time Point	Safety Analysis Set
Table 14.3.3.2.2	Potentially Clinically Important Postbaseline Biochemistry Results	Safety Analysis Set

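### The laboratory baseline (normally Day -1) may be drawn before or after food, while Day 7 and Day 14 samples come before the morning meal, so change from baseline in meal-sensitive analytes can carry a non-drug shift

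*Protocol*

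**What the plan says.** **Which sample is the baseline.** Protocol 13.3 and SAP 16.0 take the last value before the first dose. Protocol Table 2 and SAP Appendix A mark laboratory tests at Screening, Day -1, Day 7, Day 14 and Day 28, with the Day 1 cell empty. SAP 16.2 agrees: the samples "will be collected at screening, Day -1, Day 7, Day 14, and Day 28". On these schedules the baseline is normally Day -1.

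**When samples are drawn.** Footnote i to Table 2, repeated in SAP Appendix A, has samples taken at most 2 hours "prior to dosing during the Treatment Period, and any time of day at other time points". The same footnote adds: "Participants are to be in a fasted state for screening assessments only". Protocol 12.1.7 agrees: "During Screening only, samples for clinical laboratory assessments will be collected from participants when they are in a fasted state". On Days 7 and 14, participants arrive in the morning before dosing (protocol 7.1.3), and the Table 2 notes fix the order as "vital signs, ECG, blood draws, morning meal, IP dosing".

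**What is summarised.** Change from baseline in laboratory analytes is part of the secondary endpoint (protocol 6.2.2). SAP 16.2 states: "Summary tables on lab parameters will include descriptive statistics for the observed values and changes from baseline by scheduled assessment timepoint". The SAP table list includes one titled "Biochemistry Results by Time Point". Protocol Table 4 names both glucose and triglycerides.

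**The concern.** A change from baseline is easiest to read when both samples are taken under the same conditions. Here the follow-up draws at Days 7 and 14 are placed before a meal and the baseline draw is not. A site that takes the Day -1 sample after lunch complies with the protocol, and so does one that takes it before breakfast.

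All participants receive SAGE-718, so no control group shares the difference in draw conditions and allows it to be subtracted. If some Day -1 samples follow food and food raises the analyte, the mean change at Days 7 and 14 is pushed down. That could hide a real rise or look like a fall caused by the drug. At stake is the reading of one or two analytes in a large safety panel.

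**Working it through.** The documents give no figure for meal effects on laboratory values, so there is no planned number to reproduce. The check sets the rules side by side and then works out the direction of any shift.

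| Visit | Timing rule | Position relative to food | Use |
|---|---|---|---|
| Screening | Any time of day | Fasted | Baseline only if nothing later is available |
| Day -1 | Any time of day | Before or after | Normally the baseline |
| Days 7 and 14 (scheduled) | Within 2 hours before dosing, morning | Before the clinic meal; no fasting interval set | Change from baseline |
| Day 28 | Any time of day | Before or after | Change from baseline |

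The procedure order in the Table 2 notes does not protect Day -1, because no dose or protocol meal is scheduled that day.

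**Inputs, none given in the documents.**
- f: the share of Day -1 samples drawn after food (0 to 1).
- g: the same share at Day 28 (0 to 1).
- d: the mean rise in a fed sample over the same participants' pre-meal value, taken as equal at both visits.
- t: the mean amount by which a pre-meal Day -1 value exceeds a morning pre-meal value because of clock time alone.

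Assume no drug effect and the same mean pre-meal value throughout.

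**Days 7 and 14.** Expected mean change = -(f × d) - t.
- Setting t aside, the meal part runs from 0 (f = 0) to -d (f = 1). It is negative whenever f and d are both positive.
- With the planned 20 completers, each fed Day -1 sample moves the mean change by 1/20 of that participant's meal-related rise.
- If every Day -1 sample is pre-meal, the meal part is 0. The clock-time part t remains unless the draw is also in the morning.

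**Day 28, meal part only.** Expected mean change = (g - f) × d.
- Under the current rule Day 28 and Day -1 have the same freedom. If g = f the result is 0, and there is no built-in direction.
- If only Day -1 is moved to pre-meal, f = 0 and the result is +(g × d): a new upward mismatch wherever g is above 0.
- If both are moved, f = g = 0 and the result is 0.

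No value is put in for d, because none can be taken from the documents.

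**Can later data repair it?** Protocol 13.6.2 lists results with timing of collection, but clock time does not show whether the participant had eaten. The visible text describes diary recording of food only for predose intake in the Treatment Period (protocol 7.1.3). The case report form is not public and may hold more.

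**Where it shows up.** The affected displays are the observed and change-from-baseline summaries. Protocol 13.6.2 also promises a shift summary, but the visible SAP table list has none for laboratory data. The glucose limits in SAP Table 5 apply to observed values; the one limit there that uses baseline is for creatinine. SAP Table 4 as readable shows neither glucose nor triglycerides, but the table appears broken, so whether triglycerides will be displayed cannot be told.

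**The case against.** The strongest objection is that no shift has been shown. Nothing says that any Day -1 sample was taken after food, and no passage gives a meal effect for any analyte. This stands. A reader might infer that the glucose and triglyceride changes will be biased, or by how much; the documents support only that compliant conduct permits a shift.

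A second objection is that a Day 1 sample may exist. The synopsis and protocol 7.1.3 list blood and urine collection among predose procedures for Days 1, 7 and 14, and protocol 12.1.7 sets laboratory times "at the time points detailed in Table 2 and Table 3", where Table 3 is not public. A Day 1 predose sample would become the baseline, would come before the meal by procedure order, and would largely remove the problem. But the 7.1.3 sentence is a generic list for three visits and is cut in the public text, protocol 12.1 defers to Table 2, and SAP 16.2 lists no Day 1 sample. The text therefore calls for reconciliation. It does not establish that a Day 1 sample is taken, nor that the schedule is wrong.

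Third, Days 7 and 14 are themselves only loosely controlled. They are pre-meal by sequence, not fasted. Early termination and unscheduled visits can be mapped into their windows (SAP 13.10), and participants who stop treatment but keep attending (protocol 8.4.1) have no dose to time against. This is correct, and limits the point to scheduled samples in participants still on treatment.

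Finally, the timing may be too late: the SAP was signed as final on 01-Nov-2021. If collection is complete, only disclosure remains.

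**Conclusion.** The point holds as a cheap improvement. On the visible schedules, the baseline draw is free with respect to food and time of day, and the scheduled Day 7 and Day 14 draws are not. Mean change from baseline at those visits in glucose, and in triglycerides if displayed, can carry a non-drug shift. It is downward if some Day -1 samples follow food and food raises the analyte. The size cannot be estimated.

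The reach is small: descriptive summaries within a secondary endpoint, with no test. The primary endpoint and the potentially-clinically-significant flags based on observed values are unaffected.

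Two stronger readings are not supported. Day 28 does not share the directional mismatch, because it follows the same free rule as Day -1. Nor would a pre-meal Day -1 draw remove every non-drug influence: it removes the meal-timing part, a morning draw also addresses clock time, and any effect of the daily meal of about 30 g fat taken with treatment would remain.

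The conclusion assumes that no Day 1 laboratory sample is taken and that the case report form does not record meal state at Day -1.

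**What to change.** 1. Amend footnote i in protocol Table 2 and in SAP Appendix A so that the Day -1 **and** Day 28 samples are both drawn in the morning before the first meal, as on Days 7 and 14. The two must change together, for the reason shown for Day 28 above.
2. Reconcile protocol 7.1.3 and the synopsis with Table 2, SAP 16.2 and SAP Appendix A (and Table 3, if it holds laboratory time points) on whether a Day 1 predose sample is taken. If it is, name it as the baseline.
3. If samples are already collected, add a footnote to the biochemistry tables that meal state at Day -1 and Day 28 was not controlled. Change from the Screening sample is a sensitivity view at most: Screening is formally fasted and 8 to 21 days before dosing, while Days 7 and 14 are only pre-meal.

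Cost: one footnote edited in two documents, less scheduling freedom, and a morning pre-meal visit on Day -1 and Day 28. The Day -1 visit would come the day before another such visit, a real if modest burden for participants with cognitive impairment and their study partners. If data are already in hand, the cost is one table footnote.
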